#### **8.5. Subject Withdrawal Criteria and Replacement of Subjects**

Subjects have the right to withdraw from the study at any time for any reason.

Subjects may withdraw or be withdrawn from study treatment for any of the following reasons:

- Withdrawal of consent
- Experiences unacceptable toxicity
- Any medical condition, which, in the opinion of the Investigators, would put the subject at risk for continuing treatment
- Experiences disease progression (subjects who are, in the opinion of the Investigator, benefiting from treatment may be allowed to continue on study drug with approval of the Medical Monitor)
- Confirmed pregnancy (study therapy should be immediately interrupted based upon a positive urinary human chorionic gonadotropin (hCG), and permanently discontinued if confirmed by a serum  $\beta$ -hCG test)
- Development of an intercurrent medical condition that precludes further participation in the trial
- The Investigator removes the subject from the trial in the best interests of the subject
- Subject requires use of a prohibited concomitant medication ([Section 9.12.3](#))
- Protocol violation: non-adherence to study drug regimen or protocol requirements
- Lost to follow-up
- Death

Discontinuation from study treatment should be considered distinct from discontinuation from the study.

All subjects discontinued from study treatment for any reason should undergo End of Treatment (EOT) procedures, and will have a follow-up visit as described in [Section 10.1](#). All subjects discontinued from study treatment for any reason will be followed further for disease status, overall survival, and initiation of non-study anti-neoplastic therapy until death, withdrawal of consent, or the end of the study, whichever occurs first. Every attempt should be made to collect all data during the follow-up period unless subjects discontinue from the study.

Following discontinuation of study drug, all efforts will be made to complete and report the protocol-defined study observations as completely as possible and to determine the reason for withdrawal.

Once a subject has discontinued study drug (or for a subject in the expansion phase who underwent HSCT post-treatment and has subsequently relapsed and elects not to restart treatment), he or she will enter the follow-up phase for survival.

All subjects are to be followed for survival status follow up every 3 months until death, withdrawal of consent, or end of study for survival.

In the event a subject is withdrawn from study drug or the follow-up phase of the study, the Medical Monitor must be informed. If there is a medical reason for withdrawal, the subject will remain under the supervision of the Investigator until satisfactory health has returned.

When a subject discontinues study drug or withdraws from the study, the primary reason(s) for discontinuation or withdrawal must be recorded in the appropriate section of the electronic case report form (eCRF) and all efforts will be made to complete and report final study observations as thoroughly as possible.

All AEs should be followed until resolution or for a period of 28 days from the last dose of study drug, whichever is shorter. If the subject withdrew from treatment because of an AE, every effort must be made to perform protocol-specified safety follow up procedures.

Serious AEs considered related to study drug should continue to be followed until death, withdrawal of consent, or the end of the study as per [Section 11](#).

In addition, all pregnancies and suspected pregnancies (including a positive pregnancy test regardless of age or disease state) of a female subject or partner of a male subject occurring within 120 days of the subject's last dose of study drug, are considered immediately reportable events ([Section 11.3](#)).

For the dose escalation phase, subjects who do not meet the minimum treatment and safety evaluation requirements for evaluation of DLT ([Section 9.7.1](#)) and who do not experience DLT will be replaced if the minimum of 3 evaluable subjects within a cohort has not been satisfied.

- If  $\geq 2$  subjects within a cohort experience a DLT, then the previous dose level will be declared the MTD. Alternatively, a dose level intermediate between the non-tolerated dose level and the previously tolerated dose level may be explored and declared the MTD if  $< 2$  out of 6 subjects experience a DLT at that dose.

Note that if a given cohort initially enrolled 4 or 5 subjects (i.e., if there were multiple subjects in the screening process at the time the third subject within a cohort began treatment), the same rules for dose escalation apply. If 1 of the 4 (or 5 subjects) experiences a DLT, the cohort will be expanded to include a total of 6 subjects; dose escalation will occur if only 1 of 6 subjects experiences a DLT and will be halted if 2 or more subjects experiences a DLT.

Increases in the dose of AG-221 for each dose cohort will be guided by an accelerated titration design, where the dose will initially be doubled (100% increase; see [Table 1](#)) from one cohort to the next until NCI CTCAE Grade 2 or greater AG-221-related toxicity is observed in 1 subject within the cohort. Following evaluation of the event(s) by the Clinical Study Team, subsequent increases in dose will be 50% or less until the MTD is determined. The absolute percent increase in the dose will be determined by the Clinical Study Team predicated on the type and severity of any toxicity seen in the prior dose cohorts (but will never exceed 100%). Based on the emerging data, alternative dosing schedules may be explored as agreed upon by the Clinical Study Team.

The MTD is the highest dose that causes DLTs in  $< 2$  of 6 subjects.

If no DLTs are identified during the dose escalation phase, dose escalation may continue for 2 dose levels above the projected maximum clinically effective dose, as determined by an ongoing assessment of PK/PD and any observed clinical activity; this may occur in parallel with the expansion phase.

#### **9.7.1.1. Dose-limiting Toxicity**

Dose-limiting toxicities will be evaluated during Cycle 1 of treatment. Toxicities will be graded and documented according to the NCI CTCAE, Version 4.03 (see [Appendix 15.7](#)). A DLT is defined as outlined below:

##### **Non-hematologic:**

- All clinically significant non-hematologic toxicities CTCAE  $\geq$  Grade 3 with the exception of  $\geq$  Grade 3 blood bilirubin increases in subjects with a UGT1A1 mutation. In subjects with a UGT1A1 mutation, blood bilirubin increases of  $> 5 \times$  upper limit of normal (ULN) may be considered a DLT.

##### **Hematologic:**

- Prolonged myelosuppression, defined as persistence of Grade  $\geq 3$  neutropenia or thrombocytopenia (by NCI CTCAE, version 4.03, leukemia-specific criteria, i.e., marrow cellularity  $< 5\%$  on Day 28 or later from the start of study drug without evidence of leukemia) at least 42 days after the initiation of Cycle 1 therapy. Leukemia-specific grading should be used for cytopenias (based on percentage decrease from baseline: 50 to 75% = Grade 3,  $> 75\%$  = Grade 4).

Due to frequent co-morbidities and concurrent medications in the population under study, attribution of AEs to a particular drug is challenging. Therefore, all AEs that cannot clearly be

determined to be unrelated to AG-221 will be considered relevant to determining DLTs and will be reviewed by the Clinical Study Team.

The Clinical Study Team also will review any other emergent toxicities that are not explicitly defined by the DLT criteria to determine if any warrant a DLT designation.

## **9.7.2. Intra-subject Dose Modification Criteria**

### **9.7.2.1. Dose Escalation Criteria**

Intra-subject dose escalation is permitted for all subjects following Medical Monitor approval.

#### **Phase 1 Dose Escalation**

Subjects who are receiving a lower dose of AG-221 than has been evaluated and determined to be safe (i.e., following safety review of that cohort there are <2 of 6 [or 0 of 3] subjects with DLTs) may be escalated to the higher safe dose pending review with the Medical Monitor. There is no limit to the number of times the dose of AG-221 may be increased for a given subject following Medical Monitor approval.

#### **Phase 1 Part 1 Expansion**

Subjects may only be dose-escalated once from their starting dose for the following:

- suboptimal response after the first clinical response assessment or later
- evidence of relapse on AG-221 after a response either in the peripheral blood or bone marrow

#### **Phase 2**

The AG-221 dose for the subsequent treatment cycles that are given may be increased from 100 mg QD to 200 mg QD if the following occurs:

- ANC <  $0.5 \times 10^9/L$  after being on AG-221 for the first cycle without  $\geq$  Grade 3 AEs suspected by the Investigator to be related to AG-221; or
- no partial remission (PR) achieved after being on AG-221 for at least 2 cycles without  $\geq$  Grade 3 AEs suspected by the Investigator to be related to AG-221; or
- evidence of morphologic relapse or PD

If benefit is demonstrated with an increased level of dose, then that dose level should be maintained during the subsequent treatment cycles that are given. However, once increased, the AG-221 dose may be reduced if a certain level of toxicity (eg, [Section 9.7.2.2](#)) is observed and considered as possibly or probably related to AG-221 treatment. Once reduced, the AG-221 dose should not be re-escalated unless there is evidence of morphologic relapse or PD. Any subject who is unable to tolerate 50 mg QD of AG-221 should be discontinued from study treatment.

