Subjects who relapse within 1 year of initial treatment, excluding patients with favorable-risk status according to NCCN Guidelines (NCCN 2015). Favorable-risk cytogenetics: inv(16), t(16;16), t(8;21), t(15;17)The Phase 2 portion of the trial will be used to confirm the safety and clinical activity of AG-221 and to explore the relationship with PK/PD and IDH2 mutations for the treatment of subjects with relapsed or refractory AML that harbor an IDH2 mutation.

The starting dose of AG-221 recommended for evaluation for the Phase 2 portion of the trial is 100 mg QD. This is based on the safety, PK, pharmacodynamics and clinical activity of AG-221 observed to date in AG221-C-001. Evaluation of pharmacodynamic response demonstrated sustained reduction in 2-HG plasma levels by Day 1 of Cycle 2 and up to 98% inhibition in most subjects with R140Q mutation at all doses. Increasing dose is associated with higher exposure and inhibition of 2-HG in subjects with R172K mutation. Importantly, preliminary efficacy data of the 44 subjects treated at 100 mg QD has shown an overall response rate of 36.4%. Thus a dose of 100 mg should adequately achieve inhibition of 2-HG in subjects with either R140Q or R172K mutation. Moreover, the safety profile at 100 mg, including  $\geq$  Grade 3, is consistent with that of lower doses.

Subjects in the Phase 2 portion of the trial are required to have IDH2- mutation tested centrally in samples of bone marrow aspirate **and/or** peripheral blood, and confirmed positive in bone marrow aspirate **and/or** peripheral blood during screening prior to study treatment.

The purpose of this phase is to provide an assessment of its antitumor activity in subjects with AML and characterize the safety and tolerability profile.

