### **9.7.2.2. Dose Reduction Criteria**

All effort must be made to dose study drug according to schedule without cycle delay, dose interruption and reduction. Subjects will be monitored for hematologic toxicity and non-

hematologic toxicity with the National Cancer Institute (NCI) Common Terminology Criteria for Adverse Events (CTCAE, Version 4.03) used as a guide for the grading of severity.

Dose reductions to a dose approved by the Medical Monitor and/or interruption of dosing may be allowed in the event of toxicities that are assessed as possibly or probably related to treatment with AG-221 following discussion with the Medical Monitor. If the time required for recovery from toxicity, i.e., return to at least baseline levels, is more than 28 days (1 cycle), a subject's continuation in the study should be discussed with the Medical Monitor regarding the risks and benefits of continuation. The AG-221 can be dose reduced in multiples of 50 mg. For example, at a starting dose of 200 mg QD, dose reductions should occur to 150 mg QD then to 100 mg QD and then to 50 mg QD. Any subject who is unable to tolerate 50 mg QD of AG-221 should be discontinued from study treatment.

Escalation back to the starting dose and/or an intermediate dose may be permitted with Medical Monitor approval.

Subjects who experience persistent Grade  $\geq 3$  toxicity that are assessed as possibly or probably related to treatment with AG-221 who are, in the opinion of the Investigator, benefiting from treatment may be allowed to continue on study drug with approval of the Medical Monitor. If the time required for recovery from toxicity, i.e., return to at least baseline levels, is more than 28 days (1 cycle), a subject's continuation in the study should be discussed with the Medical Monitor regarding the risks and benefits of continuation.

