### **9.8.1. Guidelines for Management of QT Prolongation**

*The discussion of the emergency management of torsade de pointes and its hemodynamic consequences is beyond the scope of this guideline.*

Subjects who experience prolongation of the heart-rate corrected QT interval, Fridericia's correction (QTcF) to  $> 480$  msec (Grade  $\geq 2$ ) while treated with AG-221, should be promptly evaluated for causality of the QTc prolongation and managed according to the following guidelines:

- Levels of electrolytes (potassium, calcium, and magnesium) should be checked and supplementation given to correct any values outside the normal range.
- Concomitant therapies should be reviewed and adjusted as appropriate for medication with known QT prolonging effects.

- If no other cause is identified and the Investigator believes it is appropriate, particularly if QTc remains elevated (after above measures have been implemented, or as determined by the Investigator), investigational product may be interrupted, and an ECG should be rechecked in approximately 1 week after the QTc prolongation was first observed, or more frequently as clinically indicated.
  - If QTc has recovered or improved and the Investigator believes it is safe to do so, re-challenge with AG-221 should be considered if held. ECGs should be conducted at least weekly (eg, at every scheduled visit) for 2 weeks following QTc reduction  $\leq 480$  msec.
  - If Grade 2 (QTcF  $> 480$  and  $\leq 500$  msec), the dose of AG-221 may be reduced to a dose approved by the medical monitor without interruption of dosing. The AG-221 dose may be re-escalated to the prior dose in  $\geq 14$  days after QT prolongation has decreased to  $\leq$  Grade 1.
    - If this is the second occurrence of QT prolongation, administration of AG-221 should continue at a reduced dose (ie, the dose may not be re-escalated).
  - If Grade 3 (QTcF  $> 500$  msec), when QTc prolongation is first observed, hospitalization for continuous cardiac monitoring and evaluation by a cardiologist should both be done. Dosing with AG-221 will be interrupted. If QTc returns to within 30 ms of baseline or  $< 450$  msec within 14 days, treatment may be resumed at a reduced dose. The AG-221 dose cannot be re-escalated following dose reduction for Grade 3 QTcF prolongation unless the prolongation was associated with an electrolyte abnormality or concomitant medication.

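### For Phase 2 subjects raised to 200 mg QD and then reduced for toxicity, three protocol sections give conflicting rules on re-escalation

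*Protocol*

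**What the plan says.** Three current protocol sections deal with raising the dose again after a reduction.

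- **Protocol 9.7.2.1, Phase 2 paragraph.** The dose may go from 100 to 200 mg QD on stated grounds. The text continues "However, once increased, the AG-221 dose may be reduced if a certain level of toxicity" is seen, pointing to 9.7.2.2 as an example, and then says "Once reduced, the AG-221 dose should not be re-escalated unless there is evidence of morphologic relapse or PD".
- **Protocol 9.7.2.2, Dose Reduction Criteria.** This section carries no phase restriction. It says "Escalation back to the starting dose and/or an intermediate dose may be permitted with Medical Monitor approval", with no requirement for relapse or progression.
- **Protocol 9.8.1, QT prolongation.** This also carries no phase restriction. After Grade 2, "The AG-221 dose may be re-escalated to the prior dose in" at least 14 days from recovery to Grade 1 or lower. After a second occurrence, "administration of AG-221 should continue at a reduced dose (ie, the dose may not be re-escalated". For Grade 3, "The AG-221 dose cannot be re-escalated following dose reduction for Grade 3 QTcF prolongation", except where an electrolyte abnormality or concomitant medication was associated with it.

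The opening line of 9.7.2.1 also applies: "Intra-subject dose escalation is permitted for all subjects following Medical Monitor approval". The Phase 2 start is fixed in Protocol 7.1.3: "The starting dose of AG-221 recommended for evaluation for the Phase 2 portion of the trial is 100 mg QD".

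**The concern.** The same subject, with the same toxicity history, gets a different answer depending on which section is consulted. The disagreement runs in both directions. In some situations 9.7.2.1 is the restrictive rule and the others permit. In other situations 9.7.2.1 leaves re-escalation open and 9.8.1 closes it.

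What is at stake is how dose is managed after toxicity, including QT prolongation, and therefore subject safety. A secondary matter is the consistency of the data behind the SAP's descriptive summaries of dose intensity, relative dose intensity and dose modification (SAP 9.4 to 9.6).

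**Working it through.** This is a check of text against text, and the plan has no figure to reproduce. I applied each rule to the same hypothetical Phase 2 subjects.

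**Inputs.** Start 100 mg QD (Protocol 7.1.3). Permitted increase to 200 mg QD (9.7.2.1, Phase 2). Reductions in multiples of 50 mg (9.7.2.2), so from 200 mg the possible levels are 150, 100 and 50 mg.

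1. **Raised to 200 mg, reduced to 50 mg for related non-QT toxicity, recovered, no relapse or PD.** 9.7.2.1: do not re-escalate. 9.7.2.2: a return to the 100 mg start may be permitted with Medical Monitor approval. These conflict.
2. **Raised to 200 mg, reduced for a first Grade 2 QTcF prolongation, the 14-day recovery condition met, no relapse or PD.** 9.7.2.1: do not re-escalate. 9.8.1: return to the prior dose is allowed. These conflict.
3. **Raised to 200 mg, reduced for Grade 3 QTcF without either named cause, or for a second QT occurrence, then relapse or PD.** 9.7.2.1: its exception leaves re-escalation open. 9.8.1: not allowed, with no exception for relapse or PD. These conflict, in the opposite direction.
4. **Never raised, reduced from 100 to 50 mg.** The answer depends on the scope of the words *once reduced* in 9.7.2.1. If they continue the preceding sentence, which concerns doses already increased, 9.7.2.1 is silent here and 9.7.2.2 and 9.8.1 apply without contradiction from it. If they cover every Phase 2 reduction, cases 1 to 3 carry over.

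**Boundary of case 1.** If the subject is reduced only to 150 or 100 mg, a return to 100 mg is not an upward move. 9.7.2.2 then conflicts with 9.7.2.1 only if its in-between dose can lie above the subject's current level. The worked example in 9.7.2.2 begins from a starting dose of 200 mg QD, which is not the Phase 2 start, so it does not settle the question.

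**Precedence.** 9.7.2.1 points to 9.7.2.2 for the reduction but not for what follows it. Neither refers to 9.8.1. SAP 9.6 tabulates modifications and resolves nothing.

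**Effect on the summaries.** SAP 9.5 divides actual dose intensity by that planned from the initially assigned daily dose, here 100 mg. In case 1, each day held at 50 mg contributes 50/100 = 50% of plan, and each day back at 100 mg contributes 100/100 = 100%. The SAP reports bands of below 75%, 75 to below 90%, 90 to below 120%, and 120% or more. A subject's own band depends on days at each level, including those at 200 mg, so no overall shift can be computed.

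**The case against.** The case for leaving the text alone has five parts.

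- **Scope.** A reader might infer that every Phase 2 subject with a toxicity reduction is affected. The documents do not support that. The sentence leading into the rule concerns doses that had been increased, and re-escalation is a natural word for a dose already escalated. This stands, and it limits the certain conflict to the increased-then-reduced group. The broader reading is not excluded, because the next sentence of the same paragraph, on intolerance of 50 mg QD, applies to any subject.
- **Harmonising 9.7.2.1 and 9.7.2.2.** 9.7.2.2 speaks of the starting or an in-between dose, so it does not clearly authorise a return to 200 mg. This stands as a narrowing. It does not remove case 1.
- **QT rules as the specific exception.** Event-specific guidance beside a general rule is ordinary drafting. However, the rule in 9.7.2.1 is itself specific to Phase 2, so it is not obvious which is the general one. Even if 9.8.1 prevailed, 9.7.2.1 against 9.7.2.2 would remain.
- **Central approval.** A reader might infer that sites are free to manage the same patient in opposite ways. Medical Monitor approval, stated in the opening of 9.7.2.1 and again in 9.7.2.2, limits that. It does not dispose of the problem, because the Monitor works from the same text. For Grade 2 QT prolongation, 9.8.1 names the Monitor for choosing the reduced dose but not for the return.
- **Guidance against permission.** None of these provisions compels re-escalation, so the conflict concerns what is allowed, not what is required. That is correct as logic, but the protocol still gives different answers on what is allowed.

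**Conclusion.** The conflict is real for Phase 2 subjects raised to 200 mg QD and then reduced for toxicity: cases 1 to 3 yield incompatible answers on the visible text. For subjects reduced from the 100 mg start without a prior increase, the text is ambiguous rather than certainly contradictory.

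The documents do not say how many subjects were increased, then reduced, then considered for re-escalation, so no number can be attached. Applying an assumed reduction rate to all 125 planned Phase 2 subjects would use the wrong denominator. A reader might also infer that the response-rate result is at risk. The documents do not support that: no sample-size or primary-analysis figure depends on these rules. The consequences are for dose management, safety and descriptive dose summaries.

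The conclusion rests on the text available. Some treatment sections are redacted or absent from the public documents, so a precedence statement there cannot be excluded. It takes no position on which rule is right.

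**What to change.** Reconcile Protocol 9.7.2.1 (Phase 2), 9.7.2.2 and 9.8.1 into one consistent statement that sets out:

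- whether *once reduced* covers all Phase 2 reductions or only those following an increase;
- which section takes precedence where they differ, including QT prolongation followed by relapse or PD;
- whether Medical Monitor approval is needed for re-escalation after QT prolongation.

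Issue it to sites as a protocol clarification. The content of the rule is for the sponsor and the clinical team to decide. The cost is clarification or amendment text, with no new procedures or data.

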### **9.7.2.2. Dose Reduction Criteria**

All effort must be made to dose study drug according to schedule without cycle delay, dose interruption and reduction. Subjects will be monitored for hematologic toxicity and non-

hematologic toxicity with the National Cancer Institute (NCI) Common Terminology Criteria for Adverse Events (CTCAE, Version 4.03) used as a guide for the grading of severity.

Dose reductions to a dose approved by the Medical Monitor and/or interruption of dosing may be allowed in the event of toxicities that are assessed as possibly or probably related to treatment with AG-221 following discussion with the Medical Monitor. If the time required for recovery from toxicity, i.e., return to at least baseline levels, is more than 28 days (1 cycle), a subject's continuation in the study should be discussed with the Medical Monitor regarding the risks and benefits of continuation. The AG-221 can be dose reduced in multiples of 50 mg. For example, at a starting dose of 200 mg QD, dose reductions should occur to 150 mg QD then to 100 mg QD and then to 50 mg QD. Any subject who is unable to tolerate 50 mg QD of AG-221 should be discontinued from study treatment.

Escalation back to the starting dose and/or an intermediate dose may be permitted with Medical Monitor approval.

Subjects who experience persistent Grade  $\geq 3$  toxicity that are assessed as possibly or probably related to treatment with AG-221 who are, in the opinion of the Investigator, benefiting from treatment may be allowed to continue on study drug with approval of the Medical Monitor. If the time required for recovery from toxicity, i.e., return to at least baseline levels, is more than 28 days (1 cycle), a subject's continuation in the study should be discussed with the Medical Monitor regarding the risks and benefits of continuation.

